6.2.7. Medical History (Non-Cancer Related)

Medical history will be summarized for the safety/ITT population. Medical history data will be summarized by SOC and PT per Medical Dictionary for Regulatory Activities (MedDRA) version 22.0 or above. Patients will be counted only once for each SOC or PT in the event that they have multiple records of the same SOC or PT in the database. All medical history data will be listed.

6.2.8. Cancer-Related Medical History

Cancer-related medical history will be summarized for the safety/ITT population. Descriptive statistics on cancer-related medical history characteristics will be presented for the following:

- Number of prior regimens of anti-cancer therapies related to study indication, and time since last anti-cancer related therapy calculated as date of first dose of study treatment – stop date of last anti-cancer related therapy. For each prior regimen of anti-cancer therapies (as well as last regimen), the following will be summarized: treatment setting, medication received, best treatment response, duration of response, time to progression, type of progression and reason therapy ended.
- Prior anti-cancer surgeries related to study indication. Anatomical location, Type of procedure, reason for procedure, presence of residual disease and time since last surgery will be summarized.
- Prior anti-cancer radiotherapy related to study indication. Anatomical location, total dose and time since last radiotherapy will be summarized.
- Time since first cancer diagnosis and time since most recent progression, calculated as the date of first dose of study treatment minus date of first diagnosis. If only month and year are provided, the day=15 will be assumed. If only year is provided, month=6 and day=30 will be assumed.
- Presence of Primary Tumor at Screening
- Tumor histology/Cytology at diagnosis/screening
- Anatomical location at diagnosis/screening
- Stage Classification at diagnosis/screening
- Histopathological Grade at diagnosis/screening
- TNM Staging at diagnosis/screening
- Metastatic location at diagnosis/screening
- Distant Metastasis at diagnosis/screening

The above will also be presented in data listings by substudy and patient.

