4.2 Inclusion criteria

Each patient must meet all of the following inclusion criteria (patients may repeat the screening procedures within the screening period after initially failing to meet the clinical inclusion criteria; rescreening for molecular inclusion criteria is not permitted unless the tissue biopsy or liquid biopsy was not evaluable for technical reasons):

1. Study ICF signed by the patient indicating that they understand the purpose of, and procedures required for, the study and are willing to participate in the study, prior to any study-related procedure.
2. Male or female aged ≥ 18 years.
3. Histologically-confirmed transitional cell carcinoma of the urothelium of the upper or lower urinary tract
Note: Minor components (< 50% overall) of variant histology such as glandular or squamous differentiation, or evolution to more aggressive phenotypes such as sarcomatoid or micropapillary change, are acceptable.
4. Recurrent or progressing stage IV disease, or surgically unresectable, recurrent or progressing disease, as specified for each substudy:

- **Substudy 1:** Patients with mUC expressing *FGFR1–3* GAs who have progressed on at least one standard chemotherapy and/or immune-checkpoint blockade and have not received prior FGFR inhibiting treatment.
 - **Substudy 3:** First-line cisplatin-ineligible patients with mUC expressing *FGFR1–3* GAs, and have not received prior FGFR-inhibiting treatment.
Cisplatin-ineligibility as defined by any one of the following criteria: 1) grade ≥ 2 peripheral neuropathy; 2) CL_{CR} calculated by Cockcroft-Gault >30 mL/min but < 60 mL/min; 3) hearing impairment (measured by audiometry) of > 25 dB at two contiguous test frequencies in at least one ear; 4) comorbidity that precludes high-volume hydration.
 - **Substudy 4:** Patients with FGFR inhibitor-resistant, mUC expressing *FGFR1–3* GAs who have progressed on at least one standard regimen each of chemotherapy and immune-checkpoint blockade and have received FGFR inhibiting treatment (excluding derazantinib).
Patients assessed as having progressed upon prior treatment with FGFR inhibitors must have received FGFR inhibitor treatment for at least 12 weeks and have undergone at least one on treatment tumor imaging assessment.

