5.2.1.3 Screening visit

The screening window for clinical screening procedures will be 28 days.

At the Screening visit, clinical eligibility of prospective study participants and baseline disease status will be assessed. Patients who fail to meet the eligibility criteria should not,

under any circumstances, be enrolled into the study and must be withdrawn from the study as a screen failure.

Patients who satisfy all of the inclusion criteria (see Section 4.2) and none of the exclusion criteria (see Section 4.3) may be enrolled in the study. After written informed consent is obtained, the following will be evaluated within 28 days prior to the first dose of study treatment and documented in the eCRF:

- Demographics/medical history/baseline medical conditions (see Sections 5.3.1.1 and 5.3.1.2)
- Medical history of cancer diagnosis and treatment (see Section 5.3.1.3)
- Record prior and concomitant medications (medications used within 30 days prior to Screening) (see Section 5.3.1.4)
- Physical examination, including height, weight and vital signs (see Section 5.3.2.1)
- ECOG PS (see Inclusion criterion 7 and Section 5.3.2.2)
- Bellmunt score (see Exclusion criterion 10)
- Complete ophthalmic examination, including OCT (see Exclusion criterion 5 and Section 5.3.2.3)
- Triplicate 12-lead ECG (see Exclusion criterion 6 and Section 5.3.2.4)
- Clinical safety laboratory blood tests (see requirements in Section 5.3.2.5)

Note: CL_{CR} should be calculated by the Cockcroft-Gault equation; prothrombin time, INR, and partial thromboplastin time are required at the Screening and End of Treatment visits.

- Tuberculosis blood test (e.g., interferon- γ release assay) if clinically indicated to rule out clinical suspicion of active tuberculosis (see Exclusion criterion 17)
- Serology for human immunodeficiency virus, hepatitis B, and hepatitis C (see Exclusion criteria 15 and 16)
- Urinalysis (see Section 5.3.2.6)
- Serum pregnancy test, if applicable (see Exclusion criterion 26, Section 5.3.2.7, and Section 7.1.3).
- Tumor measurement according to RECIST 1.1 (see Section 5.3.3.2 and Appendix 2)

Note: Tumor assessments performed as SoC prior to obtaining informed consent and within 28 days of the first dose of study treatment on CID1 may be used rather than repeating tests (if tumor assessment was performed after administration of the last dose of prior anti-tumor treatment).

- Research liquid biopsy (see Section 5.3.5.1)

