6.1.4. Handling of Dropouts and Missing Data

Unless indicated otherwise, summary statistics will be reported for observed data only and missing data will not be imputed. Patients whose clinical response is unknown or not reported will be treated as non-responders.

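### SAP 6.2.8 defines time since most recent progression by the date of first diagnosis, so as written it duplicates time since diagnosis

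*SAP*

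**What the plan says.** SAP 6.2.8 (Cancer-Related Medical History) describes the cancer history to be summarised for the safety/ITT population and listed by substudy and patient. One bullet names two intervals under one formula. The first is the time since the cancer was first diagnosed; the second reads "time since most recent progression, calculated as the date of first dose of study treatment minus date of first diagnosis". Neither the SAP nor the protocol gives another formula for the progression interval.

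The same bullet then deals with partial dates: "If only month and year are provided, the day=15 will be assumed", and "If only year is provided, month=6 and day=30 will be assumed". It does not say which of the two dates these rules cover, and it sets no upper limit at first dose.

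Two other places help in reading the bullet:

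- Earlier in 6.2.8, the interval since last treatment has its own matching date: "time since last anti-cancer related therapy calculated as date of first dose of study treatment – stop date of last anti-cancer related therapy".
- SAP 6.1.4 sets the default: "Unless indicated otherwise, summary statistics will be reported for observed data only and missing data will not be imputed". The bullet in 6.2.8 is therefore an exception that stands on its own wording. The partial-date rules in SAP 6.2.6 cover medications and procedures only.

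**The concern.** A variable called time since most recent progression should run from the progression date. The formula runs from first diagnosis, so a programmer who follows the SAP would report the same quantity twice under two labels. This is a wrong derivation rule for a named output, not just a missing detail.

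The two dates will usually differ. Patients in Substudies 1 and 5 are those "who have progressed on at least one standard chemotherapy and/or immune-checkpoint blockade and have not received prior FGFR inhibiting treatment", and Substudy 4 requires progression on chemotherapy and on checkpoint blockade. For them, the most recent progression normally comes well after first diagnosis.

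The imputation rule raises a further question once the formula is corrected. A fixed mid-month or mid-year date does little harm for a diagnosis made long before entry. It is less suitable for an event that can fall shortly before treatment starts. At stake is the accuracy of one row in the baseline tables and of the matching patient listings.

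**Working it through.** The SAP states no figure here to reproduce, so the check is a reading of the formula followed by date arithmetic.

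**1. The formula as written.** Let D be the date of first diagnosis, P the date of most recent progression and F the date of first dose.

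- Time since first diagnosis, per SAP: F − D.
- Time since most recent progression, per SAP: F − D.
- Time since most recent progression, as its name implies: F − P.

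The error is (F − D) − (F − P) = P − D, the whole interval from diagnosis to latest progression. It is zero only when the two dates coincide.

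Illustration with assumed dates D = 10 May 2018, P = 2 April 2021, F = 12 April 2021:

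- As written: F − D = 1068 days.
- By name: F − P = 10 days.
- Error: 1068 − 10 = 1058 days.

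**2. Imputation, if P replaces D and the bullet's rules are applied to P.** With the same assumed dates:

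- Day missing: P becomes 15 April 2021, so F − P = −3 days.
- Year only: P becomes 30 June 2021, so F − P = −79 days.

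**3. When a negative value is possible.**

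- Day missing: F must fall before the 15th of the month of progression. P is no earlier than the 1st and F no later than the 14th, so the true lag is at most 13 days.
- Year only: F must fall before 30 June of the year of progression. P is no earlier than 1 January and F no later than 29 June, so the true lag is at most 179 days, or 180 in a leap year.

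**4. How often, given a partial date.** All first-dose dates over four years from 1 January 2021 (1460 days) were enumerated for fixed true lags. The percentages are shares of calendar dates on which the imputed interval would be negative.

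| True lag (days) | Day missing: negative | Lowest value (days) | Year only: negative | Lowest value (days) |
|---|---|---|---|---|
| 1 | 42.7% | −13 | 49.1% | −180 |
| 7 | 23.0% | −7 | 47.5% | −174 |
| 13 | 3.3% | −1 | 45.8% | −168 |
| 14 | 0% | none negative | 45.5% | −167 |
| 28 | 0% | none negative | 41.7% | −153 |
| 90 | 0% | none negative | 24.7% | −91 |
| 150 | 0% | none negative | 8.3% | −31 |
| 200 | 0% | none negative | 0% | none negative |

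These are not shares of patients. The documents do not say how many progression dates will be partial, or how long the lag to first dose will be. Protocol 5.2.1.3 gives only the length of screening: "The screening window for clinical screening procedures will be 28 days".

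**The case against.** The best defence is that this is a drafting ellipsis. The variable's name supplies its start date, the neighbouring interval since last therapy is correctly defined, and a programmer would probably query a variable that repeats the one beside it. The table shells are in a separate document (SAP 7.2), so the outputs may yet be right. This is fair as a forecast, but it does not rescue the text. If first diagnosis was meant for the first variable only, the second has no formula at all.

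A reader might infer that the variable will generally come out negative. The documents do not support that. On the literal formula no progression date is used, so none can make it negative. A negative value would then need a partial date for a very recent diagnosis, which is realistic only in first-line Substudy 3. On the corrected formula, negatives need a partial date, a short lag and imputation that extends to progression dates, which the bullet does not state. A progression just before enrolment is also the least likely to be known by year only: Protocol 5.3.1.3 asks for dates and outcomes of prior treatment. Centrally tested patients need documented progression, a liquid biopsy and a positive result before enrolment (Protocol 3.1.2), which tends to lengthen the lag.

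A reader might also infer that the error undermines comparison of these cohorts with their fixed reference response rates. Neither document uses the variable for that purpose, and SAP 6.2.8 separately summarises prior regimens, time since last therapy and time to progression on each regimen.

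**Conclusion.** The definition is wrong as written: one formula based on first diagnosis serves two different variables, and the progression interval is misstated by the full time from diagnosis to latest progression. This follows from the text alone and needs no assumption beyond the two dates differing.

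The imputation point is secondary. It rests on the assumption that the bullet's rules would be applied to progression dates, and it arises only for partial dates within the lags shown. Its frequency cannot be estimated from the documents.

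The consequence is small. The variable is descriptive. It plays no part in the response-rate decision rules (SAP 6.3.1.1), the Substudy 4 stratification (SAP 3.3) or the subgroup list (SAP 6.3.3.2). This is a correction worth making before programming is final, not a threat to any conclusion of the trial.

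**What to change.** Split the bullet in SAP 6.2.8 into two definitions:

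- Time since first cancer diagnosis: date of first dose minus date of first diagnosis (unchanged).
- Time since most recent progression: date of first dose minus date of most recent progression.

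Then state whether the partial-date rules apply to both dates, and add that an imputed date may not fall after first dose. Capping at first dose or at the day before it would both remove negative values; the choice is one of convention. It would also be sensible to prevent an imputed progression date from preceding first diagnosis.

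The cost is a few lines of SAP text and the matching programming. Sample size, visits and efficacy analyses are unaffected.

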6.2.9. Treatment Exposure and Compliance

Treatment exposure and compliance will be presented using the safety/ITT population.

Exposure to derazantinib and atezolizumab will be presented cumulatively. The number of cycles received and duration of treatment will be summarized using continuous statistics. The number of subjects with a dose reduction/interruption will be summarized as a categorical variable, including a summary of the reduced dose level achieved and the reasons for dose reduction/interruption. In addition, the total cumulative dose (mg) received will be summarized.

Dose intensity (%) will be summarised, defined as the percentage of the study drug a patient has taken compared to the amount of study drug the patient was originally planned to take at the time of their treatment allocation.

- $\% \text{ dose intensity} = \frac{\text{total cumulative dose received (mg)}}{\text{total cumulative dose planned (mg)}} \times 100$

Derazantinib treatment compliance will be presented for each cycle and overall. Compliance will be calculated by counting unused capsules:

- $\% \text{ compliance} = \frac{\# \text{ of capsules dispensed} - \# \text{ of capsules returned}}{\# \text{ of capsules prescribed} / \text{day} \times \# \text{ of days in the dosing interval}} \times 100$

Compliance will also be summarized categorically, considering cut-offs of 80% and 120% for compliance.

Day 1 for each cycle will be identified using the Visit eCRF. The number of capsules prescribed per day will be 3 (except for substudy 2 dose level 1 where 2 capsules are planned) or as determined per the dose reduction guidelines for toxicity considered related to derazantinib and specified in the eCRF. Number of days during a dosing interval will be the number of dosing days in a cycle excluding any days that the patient was instructed to hold dosing due to an AE. The periods with missed dose for any other reason are not excluded when calculating compliance. Patients with discontinuation dates that fall within cycles will have their expected days adjusted in the compliance calculation for that cycle. For example, if a patient discontinues within Week 2 of Cycle 1, the number of days in the dosing interval will be calculated based on the date of the last dose within Week 2.

The total volume and total dose of atezolizumab administered will be presented cumulatively. The number of doses where atezolizumab is administered will be summarized using continuous descriptive statistics. Treatment compliance will be presented for each dose administered. Compliance will be determined by the total dose of atezolizumab received divided by the total planned dose.

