3.1.4 Treatment period

Patients will be evaluated regularly during the treatment period as per the schedule of assessments shown in [Table 1](#). If a patient visit deviates from the permitted protocol window, the next visit must be performed at the correct timing based on the date of Cycle 1 Day 1 (C1D1).

Blood samples for PK measurements of derazantinib and atezolizumab will be collected in accordance with the schedule set out in [Table 1](#) and Section [5.3.4.1](#) (for derazantinib), and Section [5.3.4.2](#) (for atezolizumab).

Efficacy is to be evaluated by blinded independent central review (BICR) using RECIST 1.1 criteria every 9 weeks (± 7 days) for the first 27 weeks, and every 12 weeks (± 7 days) thereafter (see Section 5.3.3.2). Ideally, efficacy assessments are scheduled to permit treatment decision for D1 of the subsequent cycle.

Dose delays and/or reductions are permitted with derazantinib if a derazantinib-related toxicity is observed (see Section 6.1.1.5). No dose reductions are permitted with atezolizumab; however, dose delays are acceptable if an atezolizumab-related toxicity is observed (see Section 6.1.2.6). A related toxicity is defined as any toxicity considered related to derazantinib and/or atezolizumab, i.e., probably, or possibly related.

Substudies 3 and 5 will include a SIA for ADRs indicative of DLT (see Section 7.3.3) in the first 10 treated patients each. The process involves regular dose decision meetings (see Section 8.3.5.1). The schedule of AE assessments, including central ECGs and ophthalmological examinations, clinical safety laboratory blood sampling, and urinalysis has been expanded to a weekly schedule of assessments for the first two treatment cycles (see Table 1). Rich PK profiling will be performed for all patients during the safety run-in phase. The PK sampling schedule is provided in the Table 1.

In **Substudy 3**, if derazantinib 200 mg BID plus atezolizumab 1200 mg Q3W is considered a tolerable and safe at the safety interim analysis (endorsed by the IDMC), enrollment of Stage 1 will be completed for the efficacy interim analysis of patients. If the dose regimen is not tolerated, further enrollment will be revised and Stage 1 of Substudy 3 will enroll patients to be treated with the RP2D of derazantinib 300 mg QD plus atezolizumab 1200 mg Q3W, as determined in Substudy 2.

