4.4 Method of assignment to substudy and treatment

Patients will be assigned to a specific substudy based on the appropriate eligibility criteria.

For all substudies, a unique enrollment code will be assigned after written informed consent has been obtained, using the centralized Interactive Web Response System (IWRS). If a patient withdraws from participation in the study, his or her enrollment code will not be reused.

4.4.1 Substudy 1

All eligible patients will receive derazantinib 300 mg QD monotherapy. Treatment assignment is performed on C1D1, or as close as possible to the date on which treatment is to be administered.

4.4.2 Substudy 3

All eligible patients will receive derazantinib 200 mg BID and atezolizumab 1200 mg Q3W in combination. If derazantinib 200 mg BID at the safety interim analysis is not assessed as safe and tolerable, patients will be treated with the RP2D determined in Substudy 2 (i.e., derazantinib 300 mg QD and atezolizumab 1200 mg Q3W in combination). Treatment assignment is done on C1D1, or as close as possible to the date on which treatment is to be administered.

4.4.3 Substudy 4

Patients in **Substudy 4** are to be randomized (1:1) to receive study treatment with either derazantinib 300 mg QD monotherapy (**Cohort 4a**), or derazantinib 300 mg QD and atezolizumab 1200 mg Q3W in combination (**Cohort 4b**), based on a computer-generated randomization schedule via IWRS. Patients in Substudy 4 will be randomized on C1D1, or as close as possible to the date on which treatment is allocated. Randomization will be stratified for key prognostic factors according to the following algorithms:

- The presence of visceral metastasis, an ECOG PS of 2, or a preceding FGFR inhibitor treatment interval of less than 6 months (i.e., less than 24 full weeks) will be credited with one point, and patients will be stratified according to their composite score values of 0–1 versus 2–3 points.

4.4.4 Substudy 5

All eligible patients will receive derazantinib 200 mg BID monotherapy. Treatment assignment is performed on C1D1, or as close as possible to the date on which treatment is to be administered.

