6.1 Investigational products

6.1.1 Derazantinib

Derazantinib is an investigational drug supplied as 100 mg powder-filled capsules for oral administration.

The Investigator must ensure that derazantinib capsules will be used only in accordance with the protocol.

6.1.1.1 *Derazantinib administration*

Derazantinib capsules will be administered by mouth. The schedules for the administration of derazantinib are shown in Section 6.1.3 and Table 6.

Derazantinib capsules should be administered at least 1 hour before, or at least 2 hours after, a meal. In the event of nausea or vomiting which is assessed as CTCAE grade ≥ 2 , a light meal before subsequent derazantinib administration is allowed, to minimize the severity of the event.

6.1.1.2 *Labeling and packaging*

Derazantinib is supplied as capsules in white/opaque high-density polyethylene bottles with white/opaque polypropylene caps and labeled in the local languages as investigational agent, in accordance with local regulations and the Annex 13 Good Manufacturing Practice rules.

Labels must include the identity of the Sponsor and Investigator, patient number, protocol number, drug identification, storage conditions, content of study drug, and expiry date. Information on drug shipment including temperature logger and acknowledgement of receipt form to be completed by the receiver must also be included in the shipment.

6.1.1.3 *Drug accountability*

When a drug shipment is received, the Investigator or designee will check the amount and condition of the drug, check for appropriate local language in the label, drug expiration date, and acknowledge receipt in the IWRS system. A Packing Slip will be included with the shipment and must be completed upon receipt and returned as instructed on the form. In addition, the Investigator or designee shall contact the Sponsor as soon as possible if there is a problem with the shipment.

A Drug Accountability Log will be provided for derazantinib capsules. The log must be kept current and should contain the protocol number, the name and clinical site of the

Investigator, dates and quantities of drug received, patient's identification number to whom derazantinib capsules were dispensed, the date and quantity dispensed, and balance remaining, if from individual patient drug units, as well as the lot number, dose, and the initials of the dispenser. Drug accountability is performed to the capsule level.

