6.1.1.5 Dose modifications

In general, once the dose of derazantinib has been modified for a patient (as per [Table 4](#)), all subsequent cycles should be administered to that patient at the modified dose. The modified dose will be considered the maximum dose for all subsequent cycles for that patient.

When a drug-related toxicity is observed, dose delays and/or reductions in derazantinib administration are allowed. A drug-related toxicity is defined as any toxicity considered probably, or possibly related to derazantinib. If dose reduction is indicated, a patient should be assigned to the lower dose. Dose re-escalation is not permitted. In the event of a dose modification, the dose change(s) must be captured in the eCRF. If questions or considerations regarding dose modification arise or a specific dose modification is needed, the Sponsor's Medical Monitor or designee should be consulted.

Table 4 Derazantinib dose reduction schema

Current dose	Dose after reduction
2 capsules BID (400 mg daily)	3 capsules QD (300 mg daily)
3 capsules QD (300 mg daily)	2 capsules QD (200 mg daily)
2 capsules QD (200 mg daily)	1 capsule QD (100 mg daily)
1 capsule QD (100 mg daily)	1 capsule QOD (100 mg every other day)

Abbreviations: BID, twice a day; QD, once daily; QOD, every other day

For AEs of special interest (AESIs; see Section 7.2.6), including hyperphosphatemia and eye disorders, and any other AEs considered at least possibly derazantinib-related (see Section 7.1.1.2 for risks for derazantinib), Table 5 and Sections 6.1.1.5.1 to 6.1.1.5.3 provide specific guidance to manage these events through dose delays, reductions and/or discontinuations.

Table 5 Dose delays/reductions for drug-related toxicity

Hyperphosphatemia	
Serum phosphate level	Action
	(For serum phosphate ≥ 7.0 mg/dL, consider adding an oral phosphate binding/reducing agent until serum phosphate level returns to < 5.6 mg/dL)
< 7.0 mg/dL (< 2.26 mmol/L)	Continue derazantinib at current dose.
7.0 – 9.0 mg/dL (2.26 – 2.90 mmol/L)	Withhold derazantinib with weekly reassessments until the level returns to < 5.6 mg/dL; the patient may restart derazantinib at the dose prior to hyperphosphatemia. If hyperphosphatemia lasts > 2 weeks, consider restarting at the next lower dose.
> 9.0 – 10.0 mg/dL (> 2.90 – 3.23 mmol/L)	Withhold derazantinib with weekly reassessments until the level returns to < 5.6 mg/dL; the patient may restart at the next lower dose level.

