6.2.1 Treatment compliance for derazantinib

Derazantinib will be self-administered by the patients outside the patient's visits. All doses given during the patient's visits with the Investigator will be administered under the supervision of clinical study personnel. The patients will be instructed to return all unused derazantinib at the next visit.

Compliance to the derazantinib regimen will be evaluated by counting unused capsules.

$$\% \text{ compliance} = \frac{\# \text{ of capsules dispensed} - \# \text{ of capsules returned}}{\# \text{ of capsules prescribed/ day}^a \times \# \text{ of days}^b \text{ in the dosing interval}} \times 100$$

^a Number of capsules prescribed (i.e., 3 or as determined per the dose reduction guidelines for toxicity considered related to derazantinib and specified in the eCRF)

^b Number of days during that interval that the patient should have dosed (i.e., excluding any days that the patient was instructed to hold dosing due to an AE)

During the treatment period, if compliance is not between 80% and 120%, the patient will be counseled about the importance of adherence to the mandated regimen. If noncompliance in terms of dosing continues, the patient may have to be discontinued from the study treatment.

Administration of derazantinib capsules will be recorded in the 'Drug Accountability Log' and eCRF. Patients must return empty bottles and remaining capsules. Returned capsules must be recorded in the 'Drug Accountability Log', which is supplied to the site.

At each visit after the study treatment is initiated, the Investigator or designee must record the date, interval between visits, dose, and any dose changes/delays of study drug dispensed/administered. To avoid unnecessary waste of derazantinib capsules, in cases where treatment was interrupted and/or dose was reduced, the patient can continue dosing from the previously dispensed bottle until the next drug dispensing visit where re-supply is needed to maintain the protocol dosing regimen.

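### The derazantinib compliance formula uses 3 capsules a day, but Substudies 3 and 5 are assigned 4, so compliance on unreduced 200 mg BID is overstated by a factor of 4/3

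*SAP*

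**What the plan says.** SAP 6.2.9 defines derazantinib compliance as capsules dispensed minus capsules returned, divided by capsules prescribed per day times dosing days, times 100. On the daily count it says: "The number of capsules prescribed per day will be 3 (except for substudy 2 dose level 1 where 2 capsules are planned"). The only alternative it gives is the count after a toxicity-related reduction recorded in the eCRF. Compliance is reported per cycle, overall, and in categories cut at 80% and 120%.

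Protocol 6.2.1 uses the same formula. Its footnote reads: "Number of capsules prescribed (i.e., 3 or as determined per the dose reduction guidelines for toxicity considered related to derazantinib". It also attaches an action to the result: "if compliance is not between 80% and 120%, the patient will be counseled". Continued noncompliance may lead to discontinuation of study treatment.

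The assigned regimens are in Protocol 4.4. For Substudy 3: "All eligible patients will receive derazantinib 200 mg BID and atezolizumab 1200 mg Q3W in combination". For Substudy 5: "All eligible patients will receive derazantinib 200 mg BID monotherapy". Protocol 6.1.1 says that derazantinib is "supplied as 100 mg powder-filled capsules for oral administration". The first row of Table 4 in Protocol 6.1.1.5 gives this regimen as "2 capsules BID (400 mg daily").

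If 200 mg BID is not tolerated at the safety interim analysis of Substudy 3, Protocol 3.1.4 has further patients "treated with the RP2D of derazantinib 300 mg QD plus atezolizumab 1200 mg Q3W".

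**The concern.** A denominator of 3 suits 300 mg QD. Two of the four active substudies start at 4 capsules a day, and neither document allows for that. The reduction clause cannot supply it: 2 capsules BID is the top row of Table 4, and every reduced dose in that table is 3 capsules a day or fewer. The SAP does make an exception for the other regimen that differs from 3 (Substudy 2 dose level 1), so the constant looks like one that was not updated when the BID regimen was added.

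Substudies 3 and 5 also have a primary safety objective of confirming 200 mg BID as safe and tolerable. The compliance formula excludes only days held on instruction for an adverse event, so it is the summary that should show doses missed for other reasons. With the wrong denominator it would hide missed doses at this dose level. A site that applies the literal 3 could counsel a patient who takes every assigned capsule, and overlook one who takes about two thirds of them.

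**Working it through.** **Inputs**

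- Capsule strength: 100 mg (Protocol 6.1.1).
- Assigned dose: 200 mg BID, i.e. 400 mg a day, in Substudies 3 and 5 (Protocol 4.4.2, 4.4.4 and Table 6).
- Cycle length: 21 days (Protocol synopsis, dose and regimen).
- Denominator: 3 capsules a day, or 2 in Substudy 2 dose level 1 (SAP 6.2.9).
- Category limits: 80% and 120% (SAP 6.2.9, Protocol 6.2.1).

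**Formulas**

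- Capsules per day = daily dose / 100 mg.
- Compliance = capsules taken / (capsules prescribed per day × days) × 100, where capsules taken = dispensed − returned.

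**Where the plan's figures are right**

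- 300 mg QD: 300/100 = 3 a day; full adherence over a cycle is 63/63 = 100%.
- Substudy 2 dose level 1 (200 mg QD): 200/100 = 2 a day; 42/42 = 100%.

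**Unreduced 200 mg BID**

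- 400/100 = 4 a day, so 4 × 21 = 84 capsules expected.
- Written denominator: 3 × 21 = 63.
- Full adherence reads 84/63 = 133.3%. With 4 a day it reads 84/84 = 100%. The ratio is exactly 4/3.

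| True adherence | Reads as |
|---|---|
| 60% | 80.0% |
| 75% | 100.0% |
| 80% | 106.7% |
| 90% | 120.0% |
| 95% | 126.7% |
| 100% | 133.3% |

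Working back from the limits: 80% × 3/4 = 60% and 120% × 3/4 = 90%. True adherence from 60% up to 80% is therefore counted as within limits, and anything above 90% is counted as over the upper limit.

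**Cycle with a reduction part-way through**

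The SAP gives no rule for such a cycle. With full adherence, 10 days at 4 capsules and 11 days at 3, scored at 3 throughout, the result is (40 + 33)/63 = 73/63 = 115.9%. The inflation is smaller but still present.

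**Overall score**

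The SAP does not define how the overall figure is formed. Assume it pools capsules and days. For a fully adherent patient with a fraction f of dosing days at 4 capsules (scored against 3) and the rest at r capsules (scored against r):

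(4f + r(1 − f)) / (3f + r(1 − f)) > 1.2 gives f > 0.2r / (0.4 + 0.2r).

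- r = 3: f > 0.6/1.0 = 60%.
- r = 2: f > 0.4/0.8 = 50%.
- r = 1: f > 0.2/0.6 = 33%.

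Example over 4 cycles with a reduction to 300 mg QD: 1 cycle on BID gives 13/12 = 108.3%, 2 give 14/12 = 116.7%, and 3 give 15/12 = 125.0%.

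**The case against.** The best counter-argument is that little depends on this number. Compliance is a descriptive exposure summary. It does not define an analysis population, an endpoint, an interim rule or the DLT evaluation in Substudies 3 and 5. SAP 6.2.9 also reports cumulative dose in mg and dose intensity against the originally planned dose, and neither uses a capsule count. Drug accountability is kept to the capsule level, so compliance can be recomputed later, and a column of values near 133% would probably be noticed. A site could also read the formula's own term, capsules prescribed per day, as 4 and ignore the footnote. No comparison of compliance between substudies is planned.

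Most of that stands and limits how serious the point is. It does not remove it. Dose intensity compares with the original plan and so mixes missed doses with reductions and holds; it does not replace a compliance figure. The conspicuous values are those of adherent patients. A true 60% to 80% reads as 80% to 106.7% and looks ordinary. A programmer or site that used 4 would be departing from the written rule, which is a reason to correct the rule. The counselling consequence is conditional on a site applying the literal 3, but the footnote tells it to. Nothing can be inferred from SAP 6.8, which lists changes from the protocol: on this item the SAP and protocol agree, and both omit the BID count.

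**Conclusion.** The rule is wrong as written for dosing time on unreduced 200 mg BID. The factor of 4/3 per full cycle is exact and rests only on figures in the documents. Per-cycle, overall and categorical compliance are mis-scaled for these patients, and the 80% to 120% band corresponds to true adherence of 60% to 90%. The results for the overall score depend on the pooling assumption stated with them.

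Planned evaluable numbers are 36 in Substudy 3 and 26 in Substudy 5. The number in the safety/ITT population on BID may be higher, because non-evaluable patients are replaced, or lower, because of a Stage 1 stop or the Substudy 3 fallback.

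Substudies 1 and 4, full cycles after a reduction to 300 mg QD or lower, and Substudy 3 patients on the 300 mg QD fallback are scored correctly. The primary response analysis, the DLT model and dose intensity are unaffected. It should be corrected, but it does not threaten the main conclusions.

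**What to change.** In SAP 6.2.9 and the footnote of Protocol 6.2.1, replace the constant with the capsule count of the patient's assigned regimen: 4 a day while on 200 mg BID in Substudies 3 and 5, 3 a day on 300 mg QD, and 2 a day in Substudy 2 dose level 1. Then update it for dose reductions from the date recorded in the eCRF, so that a cycle with a part-way reduction is summed over days at each dose. Say in the SAP how the overall figure is formed, for example total capsules taken over total capsules prescribed.

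This only reconciles the formula with regimens the documents already assign. It changes no dose and no compliance limit. The cost is about one sentence in each document and one line of derivation code, with a short clause more for the overall figure.
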